6.6 Permitted dose adjustments and interruptions of study treatment

Safety and tolerability

In the event of a significant safety/tolerability concern which does not meet study stopping criteria ([Section 7.5](#)), and is not related to ALT and/or AST elevations, temporary interruption and dose adjustments are permitted as follows in order to allow the patient to continue on study treatment:

- Cohort 1: Reduction in dose frequency to every alternate day
- Cohort 2: Reduction in dose

Investigators must use their medical judgment in regards to what they deem as the best interest of the patient.

Significant isolated ALT and/or AST increase

In the event of a significant ALT and/or AST elevation, temporary interruption and dose reduction is permitted in order to allow the patient to continue on study treatment. The guidance for the modification of study treatment is outlined below and in [Table 6-3](#); this will allow an evaluation of whether such dose reductions are useful in patient management. The ability to reduce the dose is clinically relevant as data generated after dose reduction will provide further information regarding the tolerability and safety of LMB763.

If the patient has symptoms or other LFT abnormalities, in particular elevations of bilirubin and/or PT/INR and/or ALP), refer to [Section 9.3](#) and [Table 9-2](#) for appropriate actions.

Triggers related to ALT and/or AST elevation are described in [Table 9-1](#). A significant ALT and/or AST increase is defined as (i) in the presence of symptoms or other liver function abnormalities $> 3 \times \text{ULN}$, **AND in the case of elevated baseline $> 2 \times \text{Baseline value}$** ; (ii) in the absence of symptoms or other liver function abnormalities ALT and/or AST elevation $> 5 \times \text{ULN}$ **AND in the case of elevated baseline $> 2 \times \text{Baseline value}$** . All cases with ALT and/or AST elevation $> 3 \times \text{ULN}$ will be captured as a liver event per [Table 9-1](#) and instructions for further assessment detailed in [Table 9-2](#). Patients who experience significant isolated ALT and/or AST elevations will be instructed to return to the clinic within 48-72 hours for an additional laboratory evaluation to confirm these results, as defined in [Table 6-3](#). The laboratory tests to be repeated are ALT, AST, GGT, alkaline phosphatase, total bilirubin, and albumin (LFT) and PT/INR.

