The guidance for the modification of study treatment is outlined below in [Table 6-3](#).

If the additional laboratory evaluation confirms a significant increase of ALT and/or AST values, the dose frequency will be reduced to every alternate day (cohort 1), or the dose will be reduced (cohort 2); the investigator and site personnel will remain blinded to the identity of treatment. The investigator must document the patient's dose frequency reduction in source documents.

If the additional laboratory evaluation does not confirm the significant increase of ALT or AST values, the patient will continue with the assigned/original treatment.

If the additional laboratory evaluation shows a higher elevation of ALT and/or AST (e.g. > 8 x ULN) as compared to the original elevation (e.g. > 5 x ULN but < 8 x ULN), the guidance for this higher elevation (e.g. > 8 x ULN) should be followed.

Actions should be based on whichever of AST and ALT has a higher multiple of ULN or baseline value. In order to allow for variation in laboratory results, persisting elevation is defined as the value remaining at $\geq 90\%$ of the original elevated value. When there is a marked difference in multiple of ULN between ALT and AST, medical judgment should be applied to distinguish between persisting and decreasing. If at any time the repeat testing shows levels in a higher category, the guidance for the higher category should be followed.

Only one cycle of dose frequency/dose reduction is allowed. If, despite being on a reduced dose, a patient has persistent or new significant ALT and/or AST elevations, the patient must be discontinued from study treatment (refer to [Section 7.2](#)). After discontinuation for a liver-related event, LFT and clinical monitoring should continue until the event is resolved (refer to [Section 9.3](#)). Increasing the dose to the original level is not permitted.

Table 6-3 Dosing response to Isolated ALT/AST Elevations

ALT and/or AST increase	First Action	Result	2nd Action	Result	3rd Action

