> 2 x baseline AND ≤5 x ULN	Repeat tests ¹ within 48-72 hours	Elevation ² of ALT and/or AST confirmed	Initiate close observation of patient. Repeat tests ¹ within 48 – 72 hours	Persistent elevation ² of ALT and/or AST for 1 week	Cohort 1: Reduce Dose frequency to alternate day dosing Cohort 2: Reduce LMB763 dose Continue close observation of patient with minimum twice weekly testing ¹ (once weekly if stable) until ALT and AST <3x ULN (or 2x baseline if elevated before drug exposure). If ALT and AST levels remain ≥3x ULN three weeks after dose reduction, discontinue study treatment
		Decreasing ALT and AST ³		Continue assigned study treatment as per protocol	
		Decreasing ALT and AST ³	Continue assigned study treatment as per protocol	--	--
> 2 x baseline AND >5 x ULN but ≤ 8 x ULN	Repeat tests ¹ in 48 hours	Elevation ² of ALT and/or AST confirmed	Cohort 1: Reduce Dose frequency to alternate day dosing Cohort 2: Reduce LMB763 dose Initiate close observation of patient. Repeat tests ¹ within 48 – 72 hours	Persistent elevation ² of ALT and/or AST	Discontinue study treatment
		Decreasing ALT and AST ³		Continue with reduced dose frequency or reduced dose Continue close observation of patient with minimum twice weekly testing ¹ (once weekly if stable) until ALT and AST < 3 x ULN and < 2 x baseline. If ALT and AST levels remain ≥3 x ULN three weeks after dose reduction, discontinue study treatment	
		Decreasing ALT and AST ³	Continue assigned study treatment as per protocol	--	--
>2 x baseline AND >8 x ULN	Discontinue study treatment	--	--	--	--

¹Tests: A physical examination should be performed and recorded in source documents. PT/INR, ALT, AST, GGT, alkaline phosphatase, total bilirubin, and albumin; these repeats must be performed using the central laboratory if possible and captured via the unscheduled lab CRF. If this is not possible, then the repeats can be performed at a local laboratory to monitor the safety of the patient. If tests are performed at local laboratory, results will be captured in source documents only.

²Persistent: either ALT and/or AST remain > 90% of the original elevated level

³Decreasing: both ALT and AST levels decrease to ≤ 90 % of the original elevated level. Medical judgement should be applied if there is a marked difference between ALT and AST multiples

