All follow-up information, and the procedures performed must be recorded as appropriate in the CRF.

Table 9-2 Actions required for Liver Events

Criteria	Actions required	Follow-up monitoring
Potential Hy's Law case ^a	
 • Discontinue the study drug immediately • Hospitalize, if clinically appropriate • Establish causality 	ALT, AST, TBL, Alb, PT/INR, ALP and GGT until resolution ^c (frequency at investigator discretion)
ALT or AST		
$> 8 \times$ ULN and $> 2 \times$ baseline value	
 • Discontinue the study drug immediately • Hospitalize if clinically appropriate • Establish causality 	ALT, AST, TBL, Alb, PT/INR, ALP and GGT until resolution ^c (frequency at investigator discretion)
$> 3 \times$ ULN and $> 2 \times$ baseline value and INR > 1.5	
 • Discontinue the study drug immediately • Hospitalize, if clinically appropriate • Establish causality 	ALT, AST, TBL, Alb, PT/INR, ALP and GGT until resolution ^c (frequency at investigator discretion)
$> 5 \times$ ULN and $> 2 \times$ baseline value but $\leq 8 \times$ ULN	
 • Repeat LFT within 48 hours • If elevation is confirmed, refer to Table 6-3 	Refer to Table 6-3 ALT, AST, TBL, Alb, PT/INR, ALP and GGT until resolution ^c (frequency at investigator discretion)
$> 3 \times$ ULN and $> 2 \times$ baseline value, accompanied by symptoms ^b	
 • Discontinue the study drug immediately • Hospitalize if clinically appropriate • Establish causality 	Refer to Table 6-3 ALT, AST, TBL, Alb, PT/INR, ALP and GGT until resolution ^c (frequency at investigator discretion)

Criteria	Actions required	Follow-up monitoring
> 3 to ≤ 5 × ULN if normal baseline or >2 × baseline if elevated before drug exposure (patient is asymptomatic)	
 Repeat LFT within 48-72 hours If elevation is confirmed, refer to Table 6-3 	
Refer to Table 6-3
 
Investigator discretion

ALP (isolated)		
> 2 × ULN if normal baseline (in the absence of known bone pathology)	
 Repeat LFT within 48 hours If elevation persists, establish causality Complete liver CRF 	
Investigator discretion
 
Monitor LFT within 1 to 4 weeks or at next visit

TBL (isolated)		

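### Section 6.6 and row 1 of Table 6-3 disagree on when an isolated ALT/AST rise leads to dose reduction, and row 1's own entry, end-of-observation and stopping conditions do not fit together

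*Protocol*

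**What the plan says.** Protocol Section 6.6 handles isolated ALT/AST rises in running text and in Table 6-3. Section 9.3 adds Tables 9-1 and 9-2.

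- **Section 6.6, text.** A *significant* rise is defined in two ways. With "in the absence of symptoms or other liver function abnormalities ALT and/or AST elevation" must exceed 5 x ULN, and also 2 x baseline if the baseline was raised. With symptoms or other abnormalities the limit is 3 x ULN. "If the additional laboratory evaluation confirms a significant increase of ALT and/or AST values", frequency (Cohort 1) or dose (Cohort 2) is reduced. If the repeat test does not confirm it, the patient stays on the assigned treatment. Only one reduction is allowed and it cannot be undone.
- **Table 6-3, row 1.** Entry is "> 2 x baseline AND ≤5 x ULN". A rise that is confirmed and then persists for one week leads to reduction. Close observation then runs "until ALT and AST <3x ULN (or 2x baseline if elevated before drug exposure"). The next sentence reads "If ALT and AST levels remain ≥3x ULN three weeks after dose reduction, discontinue study treatment".
- **Table 6-3, row 2** (above 5 and up to 8 x ULN). The discontinuation sentence is the same, but observation runs "until ALT and AST < 3 x ULN and < 2 x baseline".
- **Table 9-2.** Asymptomatic patients are referred to Table 6-3 at "> 3 to ≤ 5 × ULN if normal baseline or >2 × baseline if elevated before drug exposure (patient is asymptomatic").
- **Table 9-1.** A value of at least 2 x baseline is a laboratory trigger, with no ULN bound and no dosing action. Section 6.6 adds that every value above 3 x ULN "will be captured as a liver event per" Table 9-1.

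**The concern.** These are dosing and stopping rules that blinded sites must apply the same way. As written, an asymptomatic patient in row 1 is reduced under the table, but the text's condition for reduction is not met. Some of those patients would be reduced at a value that the same table cell treats as low enough to end close observation. Others would be released from close observation by one sentence and taken off treatment by the next.

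A reduction is permanent, so the reading a site adopts fixes the dose the patient receives from then on. It also affects how many patients count as dose-adjusted. The SAP (Section 6.1.3) uses that number to decide whether to run an additional repeated measures ANCOVA that sets post-adjustment values to missing.

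**Working it through.** The plan gives no figure to reproduce. The rules are checked as inequalities, with all values in multiples of ULN.

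**1. Text against row 1.** Section 6.6 reduces an asymptomatic patient on a confirmed value x > 5. Row 1 reduces on 2 x baseline < x ≤ 5. No x satisfies both, so no row 1 reduction meets the text's definition of *significant*. The mismatch spans all of row 1, both below and above 3 x ULN.

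**2. No lower bound (normal baseline k ≤ 1).**
- Row 1 entry: 2k < x ≤ 5.
- Row 1 end of observation: x < 3.
- Both hold when 2k < x < 3, a width of 3 − 2k.

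| k | Range (x ULN) | Width |
|---|---|---|
| 0.5 | above 1.0 to below 3.0 | 2.0 |
| 0.75 | above 1.5 to below 3.0 | 1.5 |
| 1.0 | above 2.0 to below 3.0 | 1.0 |

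A grid in steps of 0.01 x ULN gives the same ranges (1.01–2.99, 1.51–2.99, 2.01–2.99). Table 9-2 refers a normal-baseline asymptomatic patient to Table 6-3 only for 3 < x ≤ 5, so it says nothing about these values.

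The documents give no ULN. Assuming an ALT ULN of 30 to 55 U/L, the following is illustrative only:
- ALT baseline 28 (the Cohort 2 minimum for women): 2 × 28 = 56. The range is above 56 to below 90 (3 × 30) at ULN 30, and above 56 to below 165 (3 × 55) at ULN 55.
- ALT baseline 43 (the Cohort 2 minimum for men): this is normal only if ULN is at least 43. At ULN 45 the range is above 86 (2 × 43) to below 135 (3 × 45).
- AST from 18 to 38 U/L: 38/18 = 2.11 x baseline, and at most 2.11 x ULN for any ULN of at least 18. This matters only if AST is the governing enzyme.

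**3. Overlapping end and stop conditions (elevated baseline b > 1).**
- Entry: 2b < x₀ ≤ 5, which requires b < 2.5.
- End of observation: x < 2b.
- Discontinuation at three weeks: x ≥ 3.
- Both hold when 3 ≤ x < 2b, which requires b > 1.5. The width is 2b − 3.

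| b | Three-week values meeting both | Width |
|---|---|---|
| 1.5 | none | 0 |
| 1.75 | 3.0 to below 3.5 | 0.5 |
| 2.0 | 3.0 to below 4.0 | 1.0 |
| 2.25 | 3.0 to below 4.5 | 1.5 |
| 2.5 | row 1 cannot be entered | – |

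Example: b = 2.0, entry at 4.5, three-week value 3.5. Since 3.5 < 4.0, observation ends; since 3.5 ≥ 3, treatment stops. The grid finds the overlap for b = 1.51 to 2.49. Such baselines are eligible, because exclusion criterion 18 removes only values above 5 x ULN.

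Under row 2 the end condition is x < 3 and x < 2b. That cannot coincide with x ≥ 3, so the overlap is empty for every b.

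**The case against.** **The tables have different scopes.** Table 9-2 lists actions for liver events, which for transaminases start above 3 x ULN. Table 9-1 has a separate trigger at 2 x baseline, which row 1 closely tracks. Row 1 could therefore be the response to that trigger. This stands in part. A reader might infer that Table 9-2 tells sites to keep the dose below 3 x ULN; it does not, it is silent. But the trigger carries no dosing action, so it does not show that row 1 governs, and the Section 6.6 text still points the other way.

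**Section 6.6 itself refers to Table 6-3.** Many sites would simply follow the table. That is plausible, but then the text's use of *significant* is wrong for every row 1 reduction.

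**Ending observation and stopping treatment are different acts.** A reader might infer that monitoring lapses before the stopping rule applies. The documents do not support that: Section 9.3 continues retesting of liver events until resolution, and values above 3 x ULN are liver events. What remains is a stopping condition without the elevated-baseline alternative given in the sentence before it, and a difference from row 2.

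**Row 1 has safeguards.** Reduction needs confirmation at 48–72 hours and then a week above 90% of the original value. This reduces the number of patients affected but leaves the rules inconsistent.

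**Reach is uncertain.** This stands fully and is reflected in the verdict.

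**Conclusion.** The inconsistency is real but minor. The text of Section 6.6 and row 1 differ over the whole of row 1. Row 1 can require an irreversible reduction at values between 2k and 3 x ULN that already meet its own end-of-observation limit. For 1.5 < b < 2.5 x ULN its end-of-observation and stopping conditions overlap over a width of 2b − 3.

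The number of patients affected cannot be estimated, for these reasons:
- The documents give no ULN and no frequency of such rises.
- They do not say whether a normal baseline is judged per enzyme or per patient. If per patient, many would count as elevated because of their ALT, and Table 9-2 would then refer them to Table 6-3 at 2 x baseline.
- The enzyme with the higher multiple governs, and which one that is varies by patient.
- The Cohort 2 ALT minimum is worded as applying at screening, so it does not bound the later baseline value.
- If the stopping sentence requires both enzymes to remain high, fewer patients fall in the overlap.

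A reader might go on to infer bias in the Week 12 ALT result. Nothing in the documents supports a size or direction for that, and none is claimed. The count that prompts the additional SAP analysis could vary with the reading adopted, but by an unknown amount.

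**What to change.** Reconcile Section 6.6, Table 6-3 row 1, Table 9-1 and Table 9-2:

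- Give row 1 a single entry definition, and say whether a normal or elevated baseline is judged per enzyme or per patient.
- Make row 1's entry, end-of-observation and discontinuation conditions consistent with one another for both normal and elevated baselines.
- Reword *significant* in Section 6.6 so that it expressly covers, or expressly does not cover, row 1.
- State which passage governs if text and tables differ.

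The choice of thresholds belongs to the sponsor's hepatic safety experts; none is proposed here. The cost is a protocol clarification or amendment and a notice to sites. No change to the analysis is needed.

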7.2 Discontinuation of study treatment

Patients may voluntarily discontinue study treatment for any reason at any time.

The investigator must discontinue study treatment for a given patient if, on balance, he/she believes that continuation would be detrimental to the patient's well-being.

Individual patient withdrawal:

Patients may voluntarily withdraw from the study for any reason at any time. They may be considered withdrawn if they state an intention to withdraw, fail to return for visits, or become lost to follow-up for any other reason. If a patient withdrawal occurs for any reason, the Investigator must make every effort to determine the primary reason for a patient's withdrawal from the study and record this information on the Study Completion CRF.

Individual treatment discontinuation:

Study treatment must be discontinued and the patient withdrawn from the study if the patient withdraws consent.

Study treatment must be discontinued if the following occur:

- Pregnancy.
- Hypersensitivity (CTCAE grade 2 or higher) reaction to LMB763 requiring intervention.
- Adverse events, abnormal laboratory values or abnormal test result that indicate a safety risk to the patient, in the opinion of the investigator
- An adverse event that is a CTCAE Grade 3 and believed to be related to the study drug (apart from liver and renal events - see below).
- A liver safety event as defined in [Section 9.3](#) (Liver safety monitoring) with ALT, AST, total bilirubin and/or alkaline phosphatase elevations mandating study treatment discontinuation. Please refer to [Section 9.3](#) (Liver safety monitoring), [Table 9-1](#) and [Table 9-2](#) for further instructions and monitoring.
- A renal safety event as defined in [Section 9.4](#) with serum creatinine elevations mandating study treatment discontinuation. Please refer to [Section 9.4](#) for further instructions and monitoring.
- Any protocol deviation that results in a significant risk to the patient's safety in the opinion of the investigator.
- If continuation in the study is deemed detrimental to the patient's well-being in the opinion of the investigator.

The appropriate personnel from the study site and Novartis (including the CTT, medically qualified representatives of the Sponsor, and the investigator) will assess whether study treatment should be discontinued for any patient whose treatment code has been broken inadvertently for any reason.

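### Both three-week stops in Table 6-3 literally need ALT and AST at or above 3 x ULN together, although Section 6.6 bases actions on the higher enzyme

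*Protocol*

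**What the plan says.** Table 6-3 (Protocol Section 6.6) sets the response to an isolated ALT or AST elevation. The first row covers a rise above 2 x baseline but not above 5 x ULN. The second covers a rise above 2 x baseline that lies above 5 and up to 8 x ULN. After dose reduction, each row has a condition that ends close observation and a stop at three weeks.

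- First-row end of close observation: "until ALT and AST <3x ULN (or 2x baseline if elevated before drug exposure".
- First-row stop: "If ALT and AST levels remain ≥3x ULN three weeks after dose reduction, discontinue study treatment". The second row repeats this instruction.
- Second-row end of close observation: "until ALT and AST < 3 x ULN and < 2 x baseline".
- Footnote 2, defining a persistent elevation: "either ALT and/or AST remain > 90% of the original elevated level".

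The text before the table gives a general rule: "Actions should be based on whichever of AST and ALT has a higher multiple of ULN or baseline value". It adds that on a reduced dose, if "a patient has persistent or new significant ALT and/or AST elevations, the patient must be discontinued from study treatment". In an asymptomatic patient, Section 6.6 calls an increase significant only above 5 x ULN, and above 2 x baseline if the baseline was elevated.

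**The concern.** The table chooses its conjunctions with some care. It uses an either-enzyme form for confirmed and persistent elevations, and footnote 3 requires both enzymes for a decrease. A site that reads it consistently will take the plain *and* in the stop to mean both enzymes. The general rule in Section 6.6 points the other way.

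The rule decides whether a patient stays on an investigational drug when liver enzymes have not recovered after the only dose reduction allowed. The study is multicenter, site staff are blinded and there is no data monitoring committee (Section 10.4). Two sites could therefore treat the same laboratory values differently. Section 6.6 also says that the reduction scheme is meant to show whether dose reduction is useful in managing patients. Uneven stopping would blur that.

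**Working it through.** The plan gives no figure to reproduce, so the check compares the rules directly. All values are multiples of ULN.

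**Example (first row, asymptomatic).** Take baseline ALT 1.5, peak ALT 4.8, three-week ALT 3.8 and AST 2.0.

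- Entry: 4.8 / 1.5 = 3.2, above 2 x baseline, and 4.8 is not above 5. The first row applies.
- End of close observation: 3.8 is not below 3, and 3.8 / 1.5 = 2.53 is not below 2 x baseline. Not met.
- Literal stop: ALT 3.8 ≥ 3, but AST 2.0 < 3. Not met.
- Stop on the higher enzyme: 3.8 ≥ 3. Met.
- Persistent-or-significant sentence in Section 6.6: 3.8 / 4.8 = 0.79, below 0.90, and 3.8 is not above 5. Not met.
- Table 9-2: an asymptomatic elevation in this range is referred back to Table 6-3. Immediate discontinuation above 3 x ULN needs symptoms, INR above 1.5, or raised bilirubin (potential Hy's Law).

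**Size of the window.** The other enzyme is below 3. The lower end is 3.0. The upper end is 0.9 x peak, because at or above that the elevation is persistent. It is capped at 5.0, because above that the elevation is significant. Taking persistent and significant as separate grounds for stopping is the reading kinder to the plan. The cap assumes a baseline up to 2.5. Above that, significance needs more than twice the baseline, and the second-row window can be somewhat wider.

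| Row | Peak | Upper end | Window |
|---|---|---|---|
| First | 3.3 | 0.9 x 3.3 = 2.97 | none |
| First | 4.0 | 0.9 x 4.0 = 3.60 | 3.0 to 3.6 |
| First | 4.8 | 0.9 x 4.8 = 4.32 | 3.0 to 4.3 |
| First | 5.0 | 0.9 x 5.0 = 4.50 | 3.0 to 4.5 |
| Second | 5.1 | 0.9 x 5.1 = 4.59 | 3.0 to 4.6 |
| Second | 5.5 | 0.9 x 5.5 = 4.95 | 3.0 to 4.95 |
| Second | 6 to 8 | 0.9 x peak = 5.4 to 7.2, capped at 5.0 | 3.0 to 5.0 |

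**Minor point: overlap in the first row.** Close observation can end below 2 x baseline, while the stop is a flat 3.

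- Both conditions can hold when 2 x baseline > 3, that is, baseline > 1.5.
- First-row entry (above 2 x baseline, at most 5) keeps the triggering enzyme's baseline below 5 / 2 = 2.5.
- Example: baselines ALT 2.0 and AST 1.8, three-week values 3.8 and 3.2. Then 3.8 < 4.0 and 3.2 < 3.6, so close observation may end. Both values are at least 3, so the stop also applies.
- The overlap runs from 3.0 to just under 3.6 for a baseline of 1.8, and to just under 4.0 for 2.0. Under the literal *and*, both enzymes need a baseline above 1.5. Under a one-enzyme stop, one is enough.
- The second row has no overlap, because ending observation there requires a value below 3.

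**Are such baselines eligible?** Section 4.2 excludes only ALT or AST above 5 x ULN. The documents give no ULN. Assuming 30 to 50 U/L, the minimum entry ALT for males is 60/50 = 1.2 to 60/30 = 2.0 x ULN in Cohort 1, and 43/50 = 0.86 to 43/30 = 1.43 in Cohort 2. Baselines on both sides of 1.5 can occur.

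**The case against.** The strongest reply is that Section 6.6 already answers the question. The higher-enzyme rule is stated generally and covers the three-week stop. The stop also follows directly after the condition for ending observation, so it can be read as applying whenever that condition has not been reached. This is good evidence of intent. It does not make the cell say so, and a site working from the table alone would apply the literal wording.

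The second reply is that the patient is protected in other ways, and this largely stands. The patient is on a reduced dose under close observation. Table 9-1 makes one enzyme above 3 x ULN a liver event, and Section 9.3 then calls for repeat tests two or three times weekly and consideration of interruption. Section 7.2 requires a stop for "Adverse events, abnormal laboratory values or abnormal test result that indicate a safety risk to the patient, in the opinion of the investigator". The sponsor team is unblinded throughout to monitor safety (Sections 3.1, 3.2 and 6.4). These provisions limit the harm. However, they rest on judgment, and none of them mandates the stop in the example.

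A reader might infer from the overlap that the first row orders a patient both to continue and to stop. The documents do not support that. Meeting the first condition only ends intensified observation. It does not say that treatment continues, so the express stop still governs. Nor does stopping end liver monitoring, since after discontinuation for a liver-related event "LFT and clinical monitoring should continue until the event is resolved".

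**Conclusion.** The point holds as a wording conflict in a liver-safety stopping rule, and it should be corrected. For an asymptomatic patient on the reduced dose, with one enzyme between 3.0 x ULN and the upper ends tabulated above and the other below 3 x ULN, the literal table does not stop treatment and Section 6.6 does. First-row peaks up to 3.3 x ULN are unaffected.

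A reader might go further and infer that the plan leaves patients with unresolved liver injury on drug without protection. The documents do not support that, given the evident intent of Section 6.6, the liver-event follow-up, investigator discretion and unblinded sponsor monitoring. What remains is that sites could handle the same values differently.

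The number of patients affected cannot be computed, because no dose-reduction rate is given. The first-row overlap is a minor clarity matter. It arises only for baselines above 1.5 x ULN, and how often that occurs depends on the laboratory's ULN, which is assumed here.

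**What to change.** In both three-week stop cells of Table 6-3, change the subject from *ALT and AST levels remain* to *ALT and/or AST remains*. Leave the threshold, timing and action as they are. In the first row, add one sentence: *The three-week stop takes precedence over the end of close observation.* This keeps the flat 3 x ULN ceiling. Copying the 2 x baseline allowance into the stop would also remove the overlap, but it would relax the ceiling: with a baseline of 2.4, a value of 4.7 x ULN (below 2 x 2.4 = 4.8) would stay on drug.

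The cost is a protocol amendment to the table wording, with no added visits or tests. The downside is a few more discontinuations where only one enzyme stays at or above 3 x ULN. They include a second-row patient whose enzyme has returned to a high baseline, for example baseline ALT 3.2, peak 6.6 (6.6 / 3.2 = 2.06) and back to 3.2 x ULN. Second-row entry limits the triggering enzyme's baseline to below 8 / 2 = 4.0, so this concerns baselines from 3.0 to just under 4.0. In either row, a non-triggering enzyme with a baseline at or above 3 x ULN would have the same effect. The higher-enzyme rule already implies these stops. Whether to write an exception for such baselines, and at what margin, is a choice for the sponsor's medical staff; the protocol gives no figure for it.

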- Repeating liver chemistry tests (ALT, AST, TBL, PT/INR, ALP and GGT) to confirm elevation within 48-72 hours. These liver chemistry repeats should always be performed using the central laboratory, with the results provided via the standard electronic transfer. If results will not be available from the central laboratory within 24 hours, then the repeats can also be performed at a local laboratory to monitor the safety of the patient. Should this occur, a sample should also be sent to the central laboratory for analysis. If a liver event is subsequently reported, any local liver chemistry tests previously conducted that are associated with this event should have results maintained in source documents. The result from the central laboratory will be provided via the standard electronic transfer.
- If the initial elevation is confirmed, close observation of the patient will be initiated, including consideration of treatment interruption if deemed appropriate.
- Dose adjustment, interruption and/or discontinuation of the investigational drug (refer to [Section 6.6](#) (Permitted dose adjustments and interruptions of study treatment) and [Section 7.2](#) (Discontinuation of study treatment), if appropriate
- Hospitalization of the patient if appropriate
- Causality assessment of the liver event

- Thorough follow-up of the liver event should include:
 - Repeating liver chemistry tests two or three times weekly. Testing should include PT/INR ALT, AST, ALP, and GGT. If total bilirubin is elevated $> 2 \times$ ULN, fractionation into direct and indirect bilirubin is required. To rule out muscular origin of transaminase elevations, CPK should be measured along with liver chemistry tests. Frequency of retesting can decrease to once a week or less if abnormalities stabilize or the study drug has been discontinued and the subject is asymptomatic. Retesting should be continued up to resolution.
 - Obtaining a more detailed history of symptoms and prior or concurrent diseases.
 - Obtaining a history of concomitant drug use (including nonprescription medications and herbal and dietary supplement preparations), alcohol use, recreational drug use, and special diets.
 - Exclusion of underlying liver disease, as specified in [Table 9-3](#).
 - Imaging such as abdominal US, CT or MRI, as appropriate
 - Obtaining a history of exposure to environmental chemical agents.
 - Considering gastroenterology or hepatology consultations.

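### For ALT/AST above 5 and up to 8 x ULN, Protocol Section 6.6 and Table 6-3 do not give one consistent test for whether the repeat sample confirms the elevation

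*Protocol*

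**What the plan says.** **Section 6.6, text.** A significant increase is defined by multiples of ULN and baseline. For isolated elevations the wording is "in the absence of symptoms or other liver function abnormalities ALT and/or AST elevation" above 5 x ULN, and also above 2 x baseline where baseline is elevated. The patient returns for a repeat that is to confirm the result as defined in Table 6-3. Then: "If the additional laboratory evaluation confirms a significant increase of ALT and/or AST values, the dose frequency will be reduced to every alternate day" in Cohort 1, or the dose is reduced in Cohort 2. If the repeat does not confirm, the original treatment continues. The text also defines a persisting elevation as at least 90% of the original value, to allow for laboratory variation, and bases actions on whichever of ALT and AST has the higher multiple.

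**Table 6-3, row "> 2 x baseline AND >5 x ULN but ≤ 8 x ULN".** The first repeat is sorted only by its ratio to the first value:

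- Confirmed, carrying footnote 2 ("either ALT and/or AST remain > 90% of the original elevated level"): treatment is reduced.
- Decreasing, under footnote 3 ("both ALT and AST levels decrease to ≤ 90 % of the original elevated level"): "Continue assigned study treatment as per protocol", with dashes in the remaining cells. Footnote 3 adds medical judgement where the ALT and AST multiples differ markedly.

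**Section 9.3.** Follow-up of a liver event includes "Repeating liver chemistry tests two or three times weekly". For this category Table 9-2 sends a confirmed elevation back to Table 6-3 without defining confirmed. It lists laboratory monitoring until resolution, at a frequency left to the investigator.

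**The concern.** The repeat sample is the decision point between reducing treatment and leaving it unchanged. The text defines the thing to be confirmed by an absolute level. The table judges the repeat by a relative change. These are different tests, and a sample can pass one and fail the other. A site working from the text could reduce treatment while a site working from the table continues it, on identical laboratory results.

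The patients concerned have values above 5 x ULN, a level that exclusion criterion 18 lists among the abnormalities defining hepatic decompensation or severe liver impairment. Inconsistent action would also make the record of dose adjustments harder to interpret, and SAP Sections 4 and 6.1.3 use that record.

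**Working it through.** The plan gives no figure to reproduce here, so the check applies both rules to the same repeat value. Let F be the first value and R the repeat, in multiples of ULN.

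**1. Where the two tests can disagree**

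- Text, read by its definition: still a significant increase if R > 5 (and R > 2 x baseline where baseline is elevated).
- Table: decreasing if R/F ≤ 0.9 for both enzymes.
- Both hold when 5 < R ≤ 0.9F, which requires F > 5/0.9 = 5.56.

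| F | Disputed R | Largest fall still disputed (just under) |
|---|---|---|
| 6 | >5 to 5.4 | 1 − 5/6 = 16.7% |
| 7 | >5 to 6.3 | 1 − 5/7 = 28.6% |
| 8 | >5 to 7.2 | 1 − 5/8 = 37.5% |

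Example: F = 7.9, R = 7.0, AST also at or below 90%, baseline 2 x ULN. The ratio is 7.0/7.9 = 88.6%, so the table says decreasing. R exceeds both 5 and 2 x 2 = 4, so the text's definition is still met. A patient still at 7.0 on repeat falls in the zone only if F was between 7.0/0.9 = 7.78 and 8.

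**2. Exactly 90%**

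Take F = 7.0 and R = 6.3 for the deciding enzyme, with the other enzyme at or below 90%. Section 6.6 (≥ 90%) says persisting. Footnote 2 (> 90%) says not persistent, and footnote 3 (≤ 90%) says decreasing. This does not depend on how confirm is read.

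**3. Which enzyme decides**

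Take ALT 7.5 falling to 0.85 x 7.5 = 6.375 and AST 6.0 falling to 0.95 x 6.0 = 5.7. Under Section 6.6 the higher enzyme, ALT, governs. At 85% it is not persisting. Under footnote 2 AST at 95% is enough for persistent, and under footnote 3 the result is not decreasing because both must fall. The medical-judgement clause covers only a marked difference in multiples.

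**4. How often noise alone reaches the disputed zone**

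These inputs are assumptions, not figures from the documents: within-patient CV 8% to 20%, ALT-AST correlation 0.7, no true change, log ratios bivariate normal with mean 0 and SD s = √2 x CV. ALT is the enzyme with first value F and must stay above 5.

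With a = ln(0.9)/s and b = ln(5/F)/s, P = Φ₂(a, a) − Φ₂(b, a), where Φ₂ is the bivariate normal distribution function.

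For CV 10% and F = 8: s = 0.1414, a = −0.745, b = −3.32, so P = 0.134 − 0.0004, about 13%.

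| CV | F = 5.6 | F = 6 | F = 8 | Mean over F evenly spread 5 to 8 |
|---|---|---|---|---|
| 8% | 0.6% | 5.6% | 9.6% | 6.4% |
| 10% | 0.7% | 6.1% | 13.3% | 8.2% |
| 15% | 0.6% | 5.6% | 18.6% | 9.7% |
| 20% | 0.5% | 4.7% | 19.3% | 9.1% |

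The condition that the repeat exceed 2 x an elevated baseline is not applied and would lower these figures.

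**The case against.** The best defence is that text and table form a single rule. Section 6.6 says the repeat confirms the result as defined in Table 6-3 and points to that table for treatment modification. The table attaches the 90% footnote to the confirmed outcome. On this reading, 5 x ULN selects the row and the 90% ratio decides confirmation. Nowhere does Section 6.6 say that a repeat still above 5 x ULN is by that fact confirmed. This stands: a reader might infer that Section 6.6 outright counts such a repeat as confirmed, but that is one of two available readings. It does not remove the ambiguity, because the sentence that triggers reduction speaks of confirming a significant increase, a term defined by level. Nor does it touch the conflicts at exactly 90% and over the deciding enzyme.

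A reader might also infer that a patient in the decreasing branch goes unmonitored. The documents do not support that. Every ALT or AST above 3 x ULN is captured as a liver event, and Section 9.3 and Table 9-2 supply follow-up. What is missing is a pointer from the row. The stated frequencies also differ: two or three times weekly in the Section 9.3 list, investigator discretion in Table 9-2.

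The chance that both enzymes fall by 10% or more with no true change is about 10% to 24% on the same assumptions. It would be wrong to use that as the size of the problem, because it includes repeats at or below 5 x ULN, where the two level-versus-ratio tests agree.

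Finally, whether 90% is a suitable cut-off is a clinical choice and not part of this point.

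**Conclusion.** The point holds as an inconsistency in the confirmation rule. Below 90% it is an ambiguity that can lead sites to opposite actions for first values above 5.56 x ULN. At exactly 90%, and where the two enzymes move differently, the passages conflict however confirm is read. The exact-90% clash is a single boundary value and will seldom arise; the enzyme rule is the wider of the two.

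The noise calculation puts an unchanged patient in the ambiguous zone about 6% to 10% of the time, averaged over first values spread evenly from 5 to 8 x ULN. It is under 1% at 5.6 and about 10% to 19% at 8. These figures rest on the assumed CV, correlation and spread of first values, and are before the baseline condition. The documents do not say how many patients would enter this row.

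A reader might infer that the primary ALT endpoint is biased. No such effect is shown. SAP Section 6.1.3 also plans a repeated measures analysis treating post-adjustment values as missing if the number of dose-adjusted patients is not small (for example, above 20%). The case for correction is consistent application of a hepatic-safety dosing rule.

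**What to change.** Reconcile the Section 6.6 text, the Table 6-3 row and footnotes 2 and 3 so that one stated test decides whether the repeat confirms the elevation. It needs:

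- one criterion (level, ratio, or a stated combination);
- one treatment of the 90% boundary;
- one rule for which enzyme or enzymes decide.

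Add a cross-reference from the decreasing branch of the row to the follow-up in Section 9.3 and Table 9-2, and align the testing frequency stated there. Which rule applies is for the sponsor's hepatic safety experts.

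The cost is a text amendment and a note to sites. No new procedures or data are needed.
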